6.6.1 Prior medication definition

A medication with a start date that is prior to the date of first dose of IMP will be classified as a 'prior medication'.

6.6.2 Concomitant medication definition

A medication with a start date that is on or after the date of first dose of IMP will be classified as a 'concomitant medication'.

Any medication that started prior to the first dose of IMP and continued after will be classified as both prior and concomitant. Such medications will therefore be counted in the tabulations for both prior and concomitant medication.

7 MEASUREMENTS OF TREATMENT COMPLIANCE

During the Treatment Period of this study, IMP will be administered in the clinic and compliance will be determined at the visit by study personnel.

The number of injections and volume administered for each injection at each visit will be included in the listing of study drug administration as specified in [Section 11.1](#).

Any deviations from the planned dosing schedule will be addressed at the DEMs (including evaluation of any impact on the statistical analysis) and described in the CSR. No formal calculations of compliance will be presented as all IMP is administered on site.

8 EFFICACY ANALYSES

8.1 Lesion count assessment

The primary efficacy variable and some of the exploratory efficacy variables discussed in [Section 8.3](#) (IHS4, Modified Sartorius Score, HS-Physician's Global Assessment, Hurley Stage and Erythema assessment) are based on the assessment and/or counts of different types of lesions in the following main anatomical regions at each visit.

- Inguinal (groin)
- Axillary (armpit)
- Submammary and/or intermammary in women
- Gluteal
- Other

These anatomical regions are further classified into the following locations, for the left and right sides of the body, as applicable:

- Inguinal (groin) excluding genital and pubic area – Left, Right
- Inguinal (groin) including genital and pubic area – Left, Right
- Axillary (armpit) – Left, Right
- Submammary – Left, Right
- Intermammary
- Gluteal – Buttocks – Left, Right
- Gluteal – Perianal/Perineal

All “Other” anatomical regions with lesions present will be specified in free text on the eCRF. Note that investigators will be asked to only select ‘Other’ regions with more severe lesions present.

The number of each of the following types of lesions (classified as relevant or non-relevant) will be recorded in each anatomical region, and then summed across all anatomical regions:

Relevant Lesions:

- Abscesses
- Draining tunnels (fistulas/sinus tracts)
- Inflammatory nodules

Non-relevant Lesions:

- Non-draining tunnels (fistulas/sinus tracts)
- Non-inflammatory nodules
- Hypertrophic scars

If there are 2 or more relevant lesions present in an anatomical region, the longest distance between 2 relevant lesions will be recorded and an assessment of whether these 2 relevant lesions are clearly separated by normal skin will be made.

If only 1 lesion is present in an anatomical region, then the diameter of the single lesion will be recorded.

In addition to the lesion count data, the degree of erythema will be assessed for each anatomical region and scored as follows:

- 0 = No redness
- 1 = Faint but discernible pink coloration
- 2 = Moderate red coloration
- 3 = Very red or bright red coloration

The worst overall erythema score across all anatomical regions will then be derived automatically in the database and used in the analyses.

Hurley Stage (I, II and III) will also be recorded for each anatomical area and the worst overall Hurley Stage across all anatomical regions will then be derived automatically in the database and used in the analyses.

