^o At certain sites, where feasible, representative photographs of the changes in skin will be captured. Photographs will be anonymized. Thermography (as described in [Section 13](#)) will also be performed at the same sites as photography.

^p The lesion count will be performed at every study visit and must address all relevant anatomical regions in each subject; Hurley Stage is included as an assessment performed during the lesion count. See [Section 9.3](#) for more details. The data collected from the lesion count will be used for the derivation of the HiSCR and International Hidradenitis Suppurativa Severity Score (see [Section 9.1](#) and [Section 9.2](#) for more details).

^q The Investigator or designee will contact the Interactive Response Technology for the subject identification number.

[figure not shown]
^r Randomization to IMP will occur at Baseline (Visit 2) and an Interactive Response Technology will be used for assigning eligible subjects to a treatment regimen. Subjects will be randomized 2:1:1 to bimekizumab, placebo, or adalimumab (stratified by Baseline Hurley Stage).

^s Subjects will receive assigned IMP as described in [Section 7.2](#) of the protocol. Because of differences in the dosing schedule between bimekizumab and adalimumab, a double-dummy approach will be applied such that all subjects receive 4 injections of IMP at Baseline; 2 injections of IMP at Weeks 2, 4, 6, 8, and 10; and 1 injection of IMP at Weeks 5, 7, and 9. The number of placebo and active injections will vary by visit and treatment group, as shown in Table 7-1.

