9.3 Lesion count

The lesion count is defined as a broad assessment of all the various skin “appearances” that are termed “lesions” in HS subjects. The lesion count must address all relevant anatomical regions in each subject. The lesion count will include the following:

- Abscesses (circumscribed collection of purulent exudate frequently associated with swelling and other signs of inflammation, such as fluctuance, tenderness and pain)
- Non-inflammatory fistulas (a fistula is a pathologic passageway connecting to the skin surface from dermis or sc tissue. A non-inflammatory fistula is a non-tender or minimally tender, non-erythematous fistula.)
- Draining fistulas (fistulas that drain serous or purulent fluid, either spontaneously or by gentle palpation)
- Fistulas/sinus tracts (a fistula with sinus tracts is a pathologic passageway that has developed into a channel to the skin surface)
- Non-inflammatory nodules (non-tender or minimally tender, non-erythematous nodules)
- Inflammatory nodules (a tender, erythematous, well-defined nodule. The lesion has no evidence of fluctuance. A pyogenic granuloma lesion is considered an inflammatory nodule; a papule or pustule is not considered an inflammatory nodule.)
- Hypertrophic scars (enlargement or overgrowth of a scar so that it extends above the surrounding skin surface)
- Hurley Stage assessment (see [Section 9.9](#))

The longest distance between 2 relevant lesions (if only one lesion, measure diameter of lesion) and whether the lesions are clearly separated by normal-appearing skin (yes/no) will be measured.

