8.2 Primary efficacy variable

The primary efficacy variable is the clinical response as measured by HiSCR (defined as at least a 50% reduction from Baseline in the total abscess and inflammatory nodule count [AN count], with no increase from Baseline in abscess or draining tunnel [fistula/sinus tract] count) at Week 12.

The HiSCR was developed to address issues with available HS scoring systems and is a validated variable that is responsive to improvement in disease activity, simplifies the scoring process, and increases the sensitivity to detect HS specific lesions (Kimball et al, 2014; Kimball et al, 2016b).

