8.2.1 Derivation of the primary efficacy variable

The following algorithm will be applied to derive the HiSCR at each visit, based on total lesion counts across anatomical regions for the 3 relevant lesion types recorded as specified above in [Section 8.1](#):

1. Calculate the AN count at each visit as the total number of abscesses plus the total number of inflammatory nodules, across all anatomical regions
2. Calculate the percentage change from Baseline in AN count (%ΔAN) at each visit as

$$100 \times \frac{(AN \text{ count at post-Baseline visit minus Baseline AN count})}{(\text{Baseline AN count})}$$

3. Calculate the change from Baseline in the abscess count by subtracting the Baseline abscess count from the abscess count at each post-Baseline visit
4. Calculate the change from Baseline in the draining tunnel (fistula/sinus tract) count by subtracting the Baseline draining tunnel (fistula/sinus tract) count from the draining tunnel (fistula/sinus tract) count at each post-Baseline visit
5. If the %ΔAN is less than or equal to -50%, and the change from Baseline in the abscess count is zero or negative (ie, non-positive) together with a non-positive change from Baseline in the draining tunnel (fistula/sinus tract) count, then the HiSCR will be assigned a value of 1 (ie, HiSCR is achieved); otherwise, the HiSCR will be assigned a value of 0 (ie, HiSCR is not achieved).

There will not be any imputation of missing lesion count data in the derivation of the HiSCR at any visit. In such cases the HiSCR will be missing and rules for handling missing HiSCR values in the analysis will be applied ([Section 4.2.1](#) and [Section 8.2.3](#)).

The primary efficacy variable is attained if the subject has a HiSCR of 1 at Week 12.

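### SAP 8.1 contradicts itself and the protocol on which 'Other' body regions are counted, and nothing requires HiSCR to compare the same regions at Baseline and Week 12

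*SAP*

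**What the plan says.** SAP 8.1 states that the primary variable and several exploratory ones "are based on the assessment and/or counts of different types of lesions in the following main anatomical regions at each visit". The list has four named groups (inguinal, axillary, sub/intermammary, gluteal) and 'Other'. On 'Other', two consecutive sentences read: "All “Other” anatomical regions with lesions present will be specified in free text on the eCRF", and then "Note that investigators will be asked to only select ‘Other’ regions with more severe lesions present". Lesion numbers "will be recorded in each anatomical region, and then summed across all anatomical regions".

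SAP 8.2.1 builds HiSCR on those totals: "Calculate the AN count at each visit as the total number of abscesses plus the total number of inflammatory nodules, across all anatomical regions". It then takes the change from Baseline in that count, in abscesses and in draining tunnels. Missing lesion counts are not imputed. HiSCR is then missing, and SAP 4.2.1 makes the subject a non-responder.

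Protocol 9.3 is unqualified: "The lesion count must address all relevant anatomical regions in each subject". Footnote p of Table 5-1 repeats this for every study visit. SAP 3.9, which lists departures from the protocol-defined analyses, does not mention a restriction on 'Other' regions.

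**The concern.** A within-subject change is interpretable only if the same skin is counted at both visits. If an 'Other' region is selected by its current severity, entry into the count depends on the quantity being measured. No passage in either document fixes the 'Other' regions at Baseline, requires a region once recorded to be counted again, or asks for a zero when it has cleared.

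Two errors become possible. A region severe at Baseline and milder at Week 12 may go unselected, so its remaining lesions vanish from the total, and any abscesses or draining tunnels in it vanish from the no-increase conditions. A region that is mild and omitted at Baseline may be selected once it worsens, so lesions that were already there appear new.

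The same totals feed IHS4, the AN count of 0 to 2, and disease flare. The modified Sartorius score uses the same regional records. There, an improved but not clear region that goes unselected also loses at least 5 non-count points (3 for region plus at least 2 for distance, SAP 8.3.4).

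**Working it through.** **1. The plan's own figure.** Inputs from SAP 2.4: 40 bimekizumab and 20 placebo subjects, true rates 70% and 27.6%, placebo prior Beta(5.52, 14.48), and success if the posterior P(p_BKZ > p_PBO) is at least 0.975. I summed Bin(x; 20, 0.276) × Bin(y; 40, 0.70) over all (x, y) that meet the rule, with a near-vague Beta(0.01, 0.01) prior on bimekizumab. Hurley Stage was left out as a simplification. Result: 98.7% (98.9% with a uniform prior), against the stated 'at least 99%'. The figure is reproduced to within half a point, and no input to it depends on the counting rule.

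**2. False response.** From SAP 8.2.1, %ΔAN = 100 × (post − Baseline)/Baseline, and response needs −50% or lower. The counts below are hypothetical. Lesions are inflammatory nodules, except that in the last row the 'Other' lesion is an abscess at Baseline and a nodule at Week 12. The no-increase conditions are therefore met throughout.

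| Baseline (named + Other) | Week 12 (named + Other) | All regions counted | 'Other' unselected at Week 12 |
|---|---|---|---|
| 4 + 4 = 8 | 3 + 2 | 5/8: −37.5%, no | 3/8: −62.5%, yes |
| 6 + 4 = 10 | 4 + 2 | 6/10: −40%, no | 4/10: −60%, yes |
| 8 + 2 = 10 | 5 + 1 | 6/10: −40%, no | 5/10: −50%, yes |
| 2 + 1 = 3 | 1 + 1 | 2/3: −33.3%, no | 1/3: −66.7%, yes |

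The last row is the minimum eligible AN count (Protocol 6.1, criterion 7).

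**3. General form.** If 'Other' holds a share s of the Baseline AN count and is unselected at Week 12, the named regions need a fall r with (1 − s)(1 − r) ≤ 0.5, that is r ≥ 1 − 0.5/(1 − s). For s = 10%, 20%, 30% and 40%, r is 44.4%, 37.5%, 28.6% and 16.7%, instead of a 50% fall overall.

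**4. False non-response.** Hypothetical: named regions go from 8 to 2, while an 'Other' region worsens from 2 to 3 nodules. All counted: 10 to 5, −50%, responder. With 'Other' omitted at Baseline and selected at Week 12: 8 to 5, −37.5%, non-responder.

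**5. Scale.** One misclassified subject moves the observed rate by 1/40 = 2.5 points on bimekizumab or 1/20 = 5 points on placebo. The documents give no frequency, so the sizes below are assumptions. Using the enumeration of step 1 with true HiSCR rates equal at 27.6%:

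| Spurious response added | P(success) |
|---|---|
| none | 1.2% |
| 5 points, both arms | 2.7% |
| 10 points, both arms | 4.9% |
| 5 points, bimekizumab only | 4.8% |
| 10 points, bimekizumab only | 13.6% |

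Equal inflation raises the figure because the placebo prior stays centred on 27.6%. With Beta(0.5, 0.5) priors in both arms there is no such rise (3.0% with none added, 2.6% with 10 points added to both). The bimekizumab-only rows suppose that the drug improves 'Other' regions without a true gain in HiSCR. They show sensitivity and are not estimates.

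**The case against.** The strongest reply is that the harmful reading is only one of several.

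- 'More severe' may mean the relevant lesion types that SAP 8.1 lists a few lines later (abscess, draining tunnel, inflammatory nodule). An 'Other' region with two residual inflammatory nodules would then still be counted, and a region would leave the total only when its contribution to HiSCR is truly zero. The SAP does not say that this is meant.
- SAP 8.1 does not say that 'Other' regions are reselected at each visit, or that an unselected region counts as zero. If it were handled as missing, the subject would become a non-responder, the opposite of inflation. However, SAP 8.2.1 speaks of missing counts and not of unselected regions, and SAP 8.3.8 and 8.3.9 derive worst scores over reported regions only.
- The protocol requires all relevant regions, and sites may have followed it. The working instructions are in the eCRF Completion Guidelines (Protocol 14.3.1), which are not available here. If sites did follow the protocol, the SAP sentence is wrong and should go.
- The reach is limited. The typical sites in Protocol 2.1 fall under the named regions, and assessments are made by blinded staff. Blinding does not stop a severity-driven rule from acting more often where severity changes more.

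A reader might also infer that eligibility (AN count of at least 3, no more than 20 draining fistulas) rests on an incomplete total. Those are protocol criteria applied at the Baseline Visit, and nothing ties them to the SAP 8.1 selection rule.

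**Conclusion.** The contradiction is in the text, it reaches the primary endpoint, and it should be resolved before the final analysis. Two adjacent sentences of SAP 8.1 conflict, the second also conflicts with Protocol 9.3 and Table 5-1, and no rule secures the same 'Other' regions at Baseline and Week 12. Either error can change a subject's HiSCR status with small, plausible counts.

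A reader might infer that the bimekizumab response rate is inflated. The documents do not support that. False response has more opportunity in a more effective arm because it needs improvement, but false non-response runs the other way. The share of subjects with 'Other' lesions is not given, and how sites applied the sentence is unknown. Frequency, net direction and size are therefore open. The point is a risk that the text permits, not shown misclassification, and the stated 99% probability of success does not change.

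**What to change.** **Text.** Delete the 'more severe' sentence so that SAP 8.1 agrees with Protocol 9.3. State that every 'Other' region with any abscess, inflammatory nodule or draining tunnel is counted, and that a region once recorded is counted at all later visits, with an explicit zero if clear. Align any corresponding eCRF instruction.

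**Data already collected.** This SAP amendment draws on the second interim (SAP 3.9), which was planned for when the last randomized subject had completed Week 12 or left the study, two subjects excepted (SAP 4.5.2). New counting instructions therefore come too late for nearly all Week 12 data. Instead:

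1. List by arm the subjects whose 'Other' regions differ between Baseline and Week 12, and query them against source records.
2. Add HiSCR on the named regions only, at both visits. This removes both errors but measures response on less skin.
3. Add HiSCR with a Baseline 'Other' region that has no Week 12 entry treated as missing, hence non-response. Label it a conservative bound, because truly cleared regions would also count as non-response, and present it beside item 2.

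The cost is a short SAP edit, one listing with site queries, and two extra derivations through the existing primary model. No new visits or assessments are needed.

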8.2 Primary efficacy variable

The primary efficacy variable is the clinical response as measured by HiSCR (defined as at least a 50% reduction from Baseline in the total abscess and inflammatory nodule count [AN count], with no increase from Baseline in abscess or draining tunnel [fistula/sinus tract] count) at Week 12.

The HiSCR was developed to address issues with available HS scoring systems and is a validated variable that is responsive to improvement in disease activity, simplifies the scoring process, and increases the sensitivity to detect HS specific lesions (Kimball et al, 2014; Kimball et al, 2016b).

8.2.1 Derivation of the primary efficacy variable

The following algorithm will be applied to derive the HiSCR at each visit, based on total lesion counts across anatomical regions for the 3 relevant lesion types recorded as specified above in [Section 8.1](#):

1. Calculate the AN count at each visit as the total number of abscesses plus the total number of inflammatory nodules, across all anatomical regions
2. Calculate the percentage change from Baseline in AN count (%ΔAN) at each visit as

$$100 \times \frac{(AN \text{ count at post-Baseline visit minus Baseline AN count})}{(\text{Baseline AN count})}$$

3. Calculate the change from Baseline in the abscess count by subtracting the Baseline abscess count from the abscess count at each post-Baseline visit
4. Calculate the change from Baseline in the draining tunnel (fistula/sinus tract) count by subtracting the Baseline draining tunnel (fistula/sinus tract) count from the draining tunnel (fistula/sinus tract) count at each post-Baseline visit
5. If the %ΔAN is less than or equal to -50%, and the change from Baseline in the abscess count is zero or negative (ie, non-positive) together with a non-positive change from Baseline in the draining tunnel (fistula/sinus tract) count, then the HiSCR will be assigned a value of 1 (ie, HiSCR is achieved); otherwise, the HiSCR will be assigned a value of 0 (ie, HiSCR is not achieved).

There will not be any imputation of missing lesion count data in the derivation of the HiSCR at any visit. In such cases the HiSCR will be missing and rules for handling missing HiSCR values in the analysis will be applied ([Section 4.2.1](#) and [Section 8.2.3](#)).

The primary efficacy variable is attained if the subject has a HiSCR of 1 at Week 12.

8.2.2 Primary analysis of the primary efficacy variable

The primary efficacy analysis of the primary efficacy variable will be based on the PPS.

8.2.2.1 Bayesian modeling

The primary Bayesian model (a logistic regression model for the mean binary response $E[y]$) will be:

$$\ln\left(\frac{E(y)}{1-E(y)}\right) = \beta_{PBO} X_{PBO} + \beta_{BKZ} X_{BKZ} + \beta_{ADA} X_{ADA} + \beta_{hII} X_{hII} + \beta_{hIII} X_{hIII} \quad (1)$$

where X_{PBO} , X_{BKZ} and X_{ADA} are dummy variables taking the value 1 or 0 according to whether or not each subject is in the PBO, BKZ or ADA treatment groups respectively, X_{hII} and X_{hIII} are dummy variables taking the value 1 or 0 according to whether or not each subject is in the Baseline Hurley Stage II or III groups respectively. Proof-of-concept (PoC) will be declared in this study if the estimated posterior probability, using the above model, of the difference in response rates between the BKZ and PBO treatment groups is 0.975 or greater.

For parameter estimation, the following constraint will be used:

$$\beta_{hII} = -\beta_{hIII}$$

giving the model:

$$\ln\left(\frac{E(y)}{1-E(y)}\right) = \beta_{PBO} X_{PBO} + \beta_{BKZ} X_{BKZ} + \beta_{ADA} X_{ADA} + \beta_{hII} (X_{hII} - X_{hIII}) \quad (2)$$

so that the influence of Baseline Hurley Stage on the model estimated treatment group mean responses are more evident. To see this, note that if $\bar{\eta}_{PBO}$ represents the mean of the logit responses from model (2) for the PBO subjects (the simple “arithmetic” mean) then $\text{logit}^{-1}(\bar{\eta}_{PBO})$ is the response probability associated with that mean logit response and is 1 type of estimate of the PBO group response rate. Accordingly:

- $p_{PBO} | p_{hII}^{PBO}, p_{hIII}^{PBO} = \text{logit}^{-1}(\bar{\eta}_{PBO}) = \text{logit}^{-1}(\beta_{PBO} + \beta_{hII}(p_{hII}^{PBO} - p_{hIII}^{PBO}))$ represents the probability of response in the PBO group conditional on p_{hII}^{PBO} and p_{hIII}^{PBO} , which are the Baseline Hurley Stage subject proportions chosen to evaluate the estimated PBO group mean at (here the observed proportions are chosen)
- $p_{BKZ} | p_{hII}^{BKZ}, p_{hIII}^{BKZ} = \text{logit}^{-1}(\bar{\eta}_{BKZ}) = \text{logit}^{-1}(\beta_{BKZ} + \beta_{hII}(p_{hII}^{BKZ} - p_{hIII}^{BKZ}))$ represents the probability of response in the BKZ group conditional on p_{hII}^{BKZ} and p_{hIII}^{BKZ} which are the Baseline Hurley Stage subject proportions chosen to evaluate the estimated BKZ group mean at (here again the observed proportions are chosen)
- $p_{ADA} | p_{hII}^{ADA}, p_{hIII}^{ADA} = \text{logit}^{-1}(\bar{\eta}_{ADA}) = \text{logit}^{-1}(\beta_{ADA} + \beta_{hII}(p_{hII}^{ADA} - p_{hIII}^{ADA}))$ represents the probability of response in the ADA group conditional on p_{hII}^{ADA} and p_{hIII}^{ADA} which are the Baseline Hurley stage subject proportions chosen to evaluate the estimated ADA group mean at (once more here the observed proportions are chosen)

For brevity, and unless otherwise stated the dependence of the above treatment group response rates on the chosen Baseline Hurley Stage subject proportions will be suppressed by denoting them as p_{PBO} , p_{BKZ} and p_{ADA} .

For pragmatic reasons we will ignore the Hurley stage proportions and effects in the equations for the estimated group response rates and use the following relations to map between the probability scale priors for the group response rates and the logit scale treatment group parameters

$$p_{PBO} = \text{logit}^{-1}(\beta_{PBO}) \quad (3)$$

$$p_{ADA} = \text{logit}^{-1}(\beta_{ADA}) \quad (4)$$

The expectations of the prior distributions for the PBO and ADA group response rates will be set to match the observed treatment group response rates in the PII study.

Accordingly, the priors to be used are

$$p_{PBO} \sim \beta(5.52, 14.48) \quad (5)$$

$$\beta_{BKZ} \sim N(0, 10000)$$

$$p_{ADA} \sim \beta(11.78, 8.22)$$

$$\beta_{hII} \sim N(0, 10000)$$

which have expectations equal to 28% and 59% for the PBO and ADA groups respectively to match the observed treatment group response rates of the PIONEER II study. The implicit assumption using this simple approach is that $E_{\beta_{hII}}[\beta_{hII}(p_{hII}^{BKZ} - p_{hIII}^{BKZ})] \approx 0$. It is important to recognize that even if the proposed study also observes a similar Baseline Hurley Stage effect size and subject proportions as the PIONEER II study the priors (5) and equations (3) and (4), whilst yielding estimated treatment group response rates that should be consistent with those observed in the data, may cause the estimated logit coefficients β_{PBO} and β_{ADA} to be inaccurate.

If the observed Baseline Hurley Stage effects and/or subject proportions in the proposed study are very different from those in the PIONEER II study then, and in addition to the possible invalid estimates of β_{PBO} and β_{ADA} , the estimated treatment group response rates may no longer reflect those in the data since the means of the probability scale priors will no longer match the treatment group response rate means in the observed data.

Both informative priors in (5) have been heavily discounted to account for study to study variation in both the ADA and PBO response rates, and also uncertainty in the agreement between the subject proportions and effect sizes observed in the Baseline Hurley Sage groups in the PIONEER II study and this proposed study.

To protect against severe forms of study to study variation and/or mismatches between Baseline Hurley Stage subject proportions and effect sizes, prior data conflict will be investigated for all informative priors through use of graphical displays. If there is evidence of prior data conflict for a given parameter, then a vague prior will be used for that parameter. Investigating any prior data conflict also provides some protection against model misspecification – for example if there turns out to be a Baseline Hurley Stage by treatment group interaction as the PIONEER II data suggest.

To be consistent with models used in previous UCB studies which parameterize PBO as the model intercept with the active treatment being additive effects (on the logit scale) we note that model (2) can be re-parameterized as follows:

$$\begin{aligned}\beta_{PBO} &= \gamma_{PBO} & (6) \\ \beta_{ADA} &= \gamma_{PBO} + \gamma_{ADA} \\ \beta_{BKZ} &= \gamma_{PBO} + \gamma_{BKZ} \\ \beta_{hII} &= \gamma_{hII}\end{aligned}$$

giving the model

$$\ln\left(\frac{E(y)}{1-E(y)}\right) = \gamma_{PBO} + \gamma_{BKZ} X_{BKZ} + \gamma_{ADA} X_{ADA} + \gamma_{hII}(X_{hII} - X_{hIII}) \quad (7)$$

Using this model, the process of mapping the informative priors in (5) to the logit coefficients is:

$$\begin{aligned}\beta_{PLB} &= \text{logit}(p_{PBO}) & (8) \\ \beta_{ADA} &= \text{logit}(p_{ADA}) \\ \gamma_{ADA} &= \beta_{ADA} - \beta_{PBO} \\ \gamma_{BKZ} &= \beta_{BKZ} - \beta_{PBO}\end{aligned}$$

